## **7.8 Prophylactic Medications, Treatments, and Procedures**

N/A

## **7.9 Rescue Medications, Treatments, and Procedures**

While in the chamber the patient will be attended to by an attending physician certified in hyperbaric medicine. Participants in this study are in respiratory distress and at risk for respiratory failure. If the patient develops respiratory failure, rescue therapy would be mechanical ventilation. In the event of a "code" the code team will be called and assume care of the patient upon arrival. Patients will be monitored by direct observation and cardiac monitor if indicated. Patients can be rapidly decompressed and removed from the chamber within 90 seconds if needed.

## **7.10 Participant Access to Study Agent at Study Closure**

Study team will not continue to provide the HBOT to participants once they are discharged from the hospital and completed study participation.

CONFIDENTIAL

This material is the property of the NYU School of Medicine and Langone Medical Center. Do not disclose or use except as authorized in writing by the study sponsor

Interventional Template Version: 11 January 2019

## 8 Assessment of Safety

### 8.1 Specification of Safety Parameters

We will record all adverse events for the study as described below. To assess adverse events (AEs) potentially related to HBOT, we will consider otic barotrauma, myopia, oxygen toxicity seizures and acute pulmonary edema.

### 8.2 Definition of Adverse Events (AE)

An **adverse event** (AE) is any symptom, sign, illness or experience that develops or worsens in severity during the course of the study. Intercurrent illnesses or injuries should be regarded as adverse events. Abnormal results of diagnostic procedures are considered to be adverse events if the abnormality:

- results in study withdrawal
- is associated with a serious adverse event
- is associated with clinical signs or symptoms
- leads to additional treatment or to further diagnostic tests
- is considered by the investigator to be of clinical significance

### 8.3 Definition of Serious Adverse Events (SAE)

#### Serious Adverse Event

Adverse events are classified as serious or non-serious. A **serious adverse event** is any AE that is:

- fatal
- life-threatening
- requires or prolongs hospital stay
- results in persistent or significant disability or incapacity
- a congenital anomaly or birth defect
- an important medical event

Important medical events are those that may not be immediately life threatening, but are clearly of major clinical significance. They may jeopardize the subject, and may require intervention to prevent one of the other serious outcomes noted above. For example, drug overdose or abuse, a seizure that did not result in in-patient hospitalization, or intensive treatment of bronchospasm in an emergency department would typically be considered serious.

All adverse events that do not meet any of the criteria for serious should be regarded as **non-serious adverse events**.

### 8.4 Definition of Unanticipated Problems (UP)

#### Unanticipated Problems Involving Risk to Subjects or Others

Any incident, experience, or outcome that meets all of the following criteria:

- Unexpected in nature, severity, or frequency (i.e. not described in study-related documents such as the IRB-approved protocol or consent form, the investigators brochure, etc)
- Related or possibly related to participation in the research (i.e. possibly related means there is a reasonable possibility that the incident experience, or outcome may have been caused by the procedures involved in the research)
- Suggests that the research places subjects or others at greater risk of harm (including physical, psychological, economic, or social harm).

This definition could include an unanticipated adverse device effect, any serious adverse effect on health or safety or any life-threatening problem or death caused by, or associated with, a device, if that effect, problem, or death was not previously identified in nature, severity, or degree of incidence in the

CONFIDENTIAL

This material is the property of the NYU School of Medicine and Langone Medical Center. Do not disclose or use except as authorized in writing by the study sponsor

investigational plan or application (including a supplementary plan or application), or any other unanticipated serious problem associated with a device that relates to the rights, safety, or welfare of subjects (21 CFR 812.3(s)).

## 8.5 Classification of an Adverse Event

### 8.5.1 Severity of Event

For AEs not included in the protocol defined grading system, the following guidelines will be used to describe severity.

- **Mild** – Events require minimal or no treatment and do not interfere with the participant's daily activities.
- **Moderate** – Events result in a low level of inconvenience or concern with the therapeutic measures. Moderate events may cause some interference with functioning.
- **Severe** – Events interrupt a participant's usual daily activity and may require systemic drug therapy or other treatment. Severe events are usually potentially life-threatening or incapacitating.

### 8.5.2 Relationship to Study Agent

*For all collected AEs, the clinician who examines and evaluates the participant will determine the AE's causality based on temporal relationship and his/her clinical judgment. The degree of certainty about causality will be graded using the categories below.*

- **Definitely Related** – *There is clear evidence to suggest a causal relationship, and other possible contributing factors can be ruled out. The clinical event, including an abnormal laboratory test result, occurs in a plausible time relationship to drug administration and cannot be explained by concurrent disease or other drugs or chemicals. The response to withdrawal of the drug (dechallenge) should be clinically plausible. The event must be pharmacologically or phenomenologically definitive, with use of a satisfactory rechallenge procedure if necessary.*
- **Probably Related** – *There is evidence to suggest a causal relationship, and the influence of other factors is unlikely. The clinical event, including an abnormal laboratory test result, occurs within a reasonable time after administration of the drug, is unlikely to be attributed to concurrent disease or other drugs or chemicals, and follows a clinically reasonable response on withdrawal (dechallenge). Rechallenge information is not required to fulfill this definition.*
- **Possibly Related** – *There is some evidence to suggest a causal relationship (e.g., the event occurred within a reasonable time after administration of the trial medication). However, other factors may have contributed to the event (e.g., the participant's clinical condition, other concomitant events). Although an AE may rate only as "possibly related" soon after discovery, it can be flagged as requiring more information and later be upgraded to "probably related" or "definitely related," as appropriate.*
- **Unlikely to be related** – *A clinical event, including an abnormal laboratory test result, whose temporal relationship to drug administration makes a causal relationship improbable (e.g., the event did not occur within a reasonable time after administration of the trial medication) and in which other drugs or chemicals or underlying disease provides plausible explanations (e.g., the participant's clinical condition, other concomitant treatments).*
- **Not Related** – *The AE is completely independent of study drug administration, and/or evidence exists that the event is definitely related to another etiology. There must be an alternative, definitive etiology documented by the clinician.*

### 8.5.3 Expectedness

[name] will be responsible for determining whether an AE is expected or unexpected. An AE will be considered unexpected if the nature, severity, or frequency of the event is not consistent with the risk information previously described for the study agent.

CONFIDENTIAL

This material is the property of the NYU School of Medicine and Langone Medical Center. Do not disclose or use except as authorized in writing by the study sponsor

## **8.6 Time Period and Frequency for Event Assessment and Follow-Up**

The occurrence of an AE or SAE may come to the attention of study personnel during study visits and interviews of a study participant presenting for medical care, or upon review by a study monitor. All AEs including local and systemic reactions not meeting the criteria for SAEs will be captured on the appropriate RF. Information to be collected includes event description, time of onset, clinician's assessment of severity, relationship to study product (assessed only by those with the training and authority to make a diagnosis), and time of resolution/stabilization of the event. All AEs occurring while on study must be documented appropriately regardless of relationship. All AEs will be followed to adequate resolution.

Any medical condition that is present at the time that the participant is screened will be considered as baseline and not reported as an AE. However, if the study participant's condition deteriorates at any time during the study, it will be recorded as an AE. UPs will be recorded in the data collection system throughout the study.

Changes in the severity of an AE will be documented to allow an assessment of the duration of the event at each level of severity to be performed. AEs characterized as intermittent require documentation of onset and duration of each episode.

The PI will record all reportable events with start dates occurring any time after informed consent is obtained until 7 (for non-serious AEs) or 30 days (for SAEs) after the last day of study participation. At each study visit, the investigator will inquire about the occurrence of AE/SAEs since the last visit. Events will be followed for outcome information until resolution or stabilization.

All unresolved adverse events should be followed by the investigator until the events are resolved, the subject is lost to follow-up, or the adverse event is otherwise explained. At the last scheduled visit, the investigator should instruct each subject to report any subsequent event(s) that the subject, or the subject's personal physician, believes might reasonably be related to participation in this study. The investigator should notify the study sponsor of any death or adverse event occurring at any time after a subject has discontinued or terminated study participation that may reasonably be related to this study. The sponsor should also be notified if the investigator should become aware of the development of cancer or of a congenital anomaly in a subsequently conceived offspring of a subject that has participated in this study.

## **8.7 Reporting Procedures – Notifying the IRB**

### **Adverse Event Reporting:**

Adverse Events will be documented on the appropriate Case Report Form (CRF) as the Investigator learns of the event. The Investigator will follow all AEs until adequate resolution is achieved. The IRB should be notified of all AEs according to their notification policies.

### **Serious Adverse Event Reporting**

In the case of a SAE, the Investigator must notify IRB according to their notification policies. All SAEs will be followed until satisfactory resolution or until the site Investigator deems the event to be chronic or the adherence to be stable. Other supporting documentation of the event may be requested by the IRB should be provided as soon as possible.

### **Unanticipated Adverse Device Effect Reporting**

An Investigator shall submit to the reviewing IRB a report of any UADE occurring during an investigation as soon as possible, but in no event later than 10 working days after the investigator first learns of the effect [21 CFR 812.150(a)(1)].

Investigators must report possible Unanticipated Problems to the IRB promptly. If the event requires immediate intervention to prevent serious harm to subjects or others, the investigator may act accordingly to prevent harm and then must report the event within five (5) days.

CONFIDENTIAL

This material is the property of the NYU School of Medicine and Langone Medical Center. Do not disclose or use except as authorized in writing by the study sponsor

Investigators must report all other possible Unanticipated Problems occurring at the local research site and non-local research sites to the IRB as soon as possible but no later than ten (10) business days from the date of the event or from the date the investigator is notified of the event.

### **8.7.1 Adverse Event Reporting**

The research coordinator on the study team will record all reportable adverse events with start dates occurring any time after informed consent is obtained. The investigator will inquire about the occurrence of adverse events or serious adverse events. In addition, all study participants will receive the telephone number to contact the research coordinator directly, who will inform the Principal Investigator of any events that may be related to the HBOT immediately. As the Principal Investigator specializes in hyperbaric medicine, he will contact the study participant directly to obtain additional information about the event and what medical attention the study participant should seek if needed. Events will be followed for outcome information until resolution or stabilization. All adverse events and serious adverse events will be reported to Institutional Review Board (IRB) according to the local IRB reporting guidelines.

### **8.7.2 Serious Adverse Event Reporting**

The research coordinator on the study team will record all reportable serious adverse events with start dates occurring any time after informed consent is obtained. The investigator will inquire about the occurrence of adverse events or serious adverse events. In addition, all study participants will receive the telephone number to contact the research coordinator directly, who will inform the Principal Investigator of any events immediately. As the Principal Investigator specializes in hyperbaric medicine, he will contact the study participant directly to obtain additional information about the event and what medical attention the study participant should seek if needed. Events will be followed for outcome information until resolution or stabilization. All adverse events and serious adverse events will be reported to Institutional Review Board (IRB) according to the local IRB reporting guidelines. We plan on addressing these events expediently and making sure that other study participants are aware of any new risks identified during the course of the study intervention.

### **8.7.3 Unanticipated Problem Reporting**

Incidents or events that meet the OHRP criteria for UPs require the creation and completion of an UP report form. It is the site investigator's responsibility to report UPs to their IRB. The UP report will include the following information:

- Protocol identifying information: protocol title and number, PI's name, and the IRB project number;
- A detailed description of the event, incident, experience, or outcome;
- An explanation of the basis for determining that the event, incident, experience, or outcome represents an UP;
- A description of any changes to the protocol or other corrective actions that have been taken or are proposed in response to the UP.

To satisfy the requirement for prompt reporting, UPs will be reported using the following timeline:

- UPs that are SAEs will be reported to the IRB within 48 hours of the investigator becoming aware of the event.
- Any other UP will be reported to the IRB in accordance with the local IRB reporting guidelines
- All UPs should be reported to appropriate institutional officials (as required by an institution's written reporting procedures), the supporting agency head (or designee), and OHRP within 5 days of the IR's receipt of the report of the problem from the investigator.

### **8.7.4 Reporting of Pregnancy**

Pregnant patients will not be enrolled.

CONFIDENTIAL

This material is the property of the NYU School of Medicine and Langone Medical Center. Do not disclose or use except as authorized in writing by the study sponsor

Interventional Template Version: 11 January 2019

## **8.8 Reporting Procedures – Notifying the Study Sponsor**

N/A

## **8.9 Reporting Procedures – Notifying the FDA**

NYU's Manager of Research Regulatory Affairs determined that your study using HBOT chambers is considered a non-significant risk (NSR) device based on the following:

1. The device is not intended as an implant
2. The device is purported or represented to be for a use in supporting or sustaining human life ("to rescue 20 patients with respiratory failure caused by COVID-19"), but it does not present a potential for serious risk to the health, safety, or welfare of a subject
3. The device is for a use of substantial importance in mitigating disease ("to rescue patients with 30 respiratory distress caused by COVID-19"), but does not present a potential for serious risk to the health, safety, or welfare of a subject
4. The device otherwise does not present a potential for serious risk to the health, safety, or welfare of a subject

Therefore, an Investigational Device Exemption application does not need to be submitted to the U.S Food and Drug Administration (FDA).

## **8.10 Reporting Procedures – Participating Investigators**

N/A

## **8.11 Study Halting Rules**

Administration of study device will be halted in the event of the following:

- If the study team deems that transport or treatment of patients in the hyperbaric unit significantly increases the risk of respiratory failure
- If any patient experiences a death which is likely to be attributable to the use of HOBT.

## **8.12 Safety Oversight**

It is the responsibility of the co-Principal Investigators to oversee the safety of the study at his/her site. This safety monitoring will include careful assessment and appropriate reporting of adverse events as noted above, as well as the construction and implementation of a site data and safety-monitoring plan. Medical monitoring will include a regular assessment of the number and type of serious adverse events.

### **Data Safety Monitoring Plan (DSMP)**

Safety oversight will be under the direction of the co-Principal Investigators and co-Investigators at each site independently with statistical assistance as needed from our site by sending deidentified data. After the first 10 patients complete the protocol, a pause in enrollment will be initiated and the data will be reviewed to ensure all adverse events were reviewed.

The investigators will meet after 10, 20, and 40 patients complete the protocol to assess safety and efficacy data on each arm of the study. Events that will be monitored are 1. need for mechanical ventilation 2. upgrade in level of care 3. seizure activity and 4. death.

Investigators from all sites will report SAE and AE to the co-Principal Investigators in addition to conducting their own reviews, and the co-Principal Investigators will meet every three weeks to review data with weekly meetings as needed.

### **Clinical Monitoring**

Clinical site monitoring is conducted to ensure that the rights and well-being of human subjects are protected, that the reported trial data are accurate, complete, and verifiable, and that the conduct of the trial is in compliance with the currently approved protocol/amendment(s), with GCP, and with applicable regulatory requirement(s).

CONFIDENTIAL

This material is the property of the NYU School of Medicine and Langone Medical Center. Do not disclose or use except as authorized in writing by the study sponsor

Interventional Template Version: 11 January 2019

- Monitoring for this study will be performed by co-investigators and study coordinators.
- Initial assessment of data quality and safety will be conducted after first enrollment.
- Further monitoring be conducted throughout the study of targeted data verification of endpoint, safety and other key data variables.
- Monitoring will occur on a weekly basis once patients are enrolled with emphasis on the predefined stopping points. Reviews will be disseminated at the weekly research meeting.

## 9 Statistical Considerations

### 9.1 Statistical and Analytical Plans (SAP)

A formal SAP will be prepared at the end of the study, the study is non-blinded.

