Description of Study Agent/Procedure	
Hyperbaric oxygen therapy involves placing patients in an enclosed chamber with 100% inhaled oxygen at an increased atmospheric pressure. HBOT chambers have shown efficacy and been cleared by the FDA for 13 conditions:
 
 
• Air or gas embolism
 
• Carbon monoxide poisoning
 
• Clostridial myositis and myonecrosis (gas gangrene)
 
• Crush injury, compartment syndrome, and other acute traumatic ischemias
 
• Decompression sickness
 
• Enhancement of healing in conditions including:                     
 
◦ Diabetically derived illness, such as diabetic foot, diabetic retinopathy, diabetic nephropathy
 
◦ Exceptional blood loss (anemia)
 
◦ Intracranial abscess
 
◦ Necrotizing soft tissue infections (necrotizing fasciitis)
 
◦ Osteomyelitis (refractory)
 
◦ Delayed radiation injury (soft tissue and bony necrosis)
 
◦ Skin grafts and flaps (compromised)
 
◦ Thermal burns
 
 
 

Reference Therapy	
Standard of care matched cohort of patients that did not receive HBOT based on age and gender and if possible underlying medical comorbidities and initial disease severity.

Key Procedures	
 
• Hyperbaric Oxygen Treatment
 
• Review of standard of care pre and post treatment blood draws to evaluate the blood oximetry along with markers of inflammation (e.g., D-dimer, Lymphocytes, IL-6, Ferritin, LDH, CRP, ESR, Fibrinogen, and troponin)
 
• Chart review
 

Statistical Analysis	
For binary primary and secondary endpoints, chi-squared analysis of proportions between the two matched groups with multivariate logistic regression if we find identifiable differences in the two study arms. T-test and linear regression for secondary endpoints that are continuous variables.

CONFIDENTIAL

This material is the property of the NYU School of Medicine and Langone Medical Center. Do not disclose or use except as authorized in writing by the study sponsor

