## **4 Study Design and Endpoints**

### **4.1 Description of Study Design**

This is a multi-center prospective pilot cohort study to evaluate the safety and efficacy of hyperbaric oxygen therapy (HBOT) as an emergency investigational device for treating patients with a novel coronavirus, disease, COVID-19. Patients that meet inclusion criteria will be consented by the hyperbaric physician. They will then be transported from the ED or other unit to the hyperbaric unit maintaining airborne precautions based on the most current hospital protocol. All study personnel will have proper PPE at all times. The patient will then be placed into the monoplace chamber and when the chamber door is closed the patient will remove any respiratory filter/mask that was placed. The patient will receive 90 minutes of hyperbaric oxygen at 2.0 ATA with or without airbreaks per the hyperbaric physician. Upon completion of the treatment the patient will then return to the medical unit and continue all standard of care. Additional treatments (up to 5 total) can be given if warranted and agreed upon by the patient and all members of the team caring for the patient. An interim analysis after the 1st 10 patients will be conducted for all endpoints. During the interim analysis of the first 10 patients and after the intervention portion of this study, a chart review will be performed to compare the outcomes of intervention patients versus age and gender matched control patients who received standard of care.

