### 9.4 Description of Statistical Methods

#### 9.4.1 General Approach

We will summarize the continuous variables using mean, median, standard deviation and ranges, and the categorical variables using frequency and proportions. Variables will also be summarized graphically. Baseline characteristics of the participants who received HBOT will be compared with that of control patients receiving SOC. If we find any significant difference in the baseline variables between the two matched groups, we will adjust for them as covariates in outcome analysis. T-test or ANOVA will be used for continuous variables whereas chi-squared test will be used for comparison of proportions. All tests will be two tailed at significance level of 0.05. Appropriate transformations (such as log transformation) will be considered for any continuous variable that indicates non-normality. Statistical software R and SAS will be used for the analysis.

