#### 9.4.2 Analysis of the Primary Efficacy Endpoint(s)

The primary endpoint will be patient mortality, a binary outcome variable indicating whether a patient died during hospitalization for COVID treatment. We will compute proportion of patients who died in each

CONFIDENTIAL

This material is the property of the NYU School of Medicine and Langone Medical Center. Do not disclose or use except as authorized in writing by the study sponsor

matched group. Chi-squared test will be utilized to compare rates of incident mortality in each group. We will also report estimates of difference in proportions along with an estimate of uncertainty using 95% confidence interval.

As a follow-up analysis, we will use a multivariable logistic regression, adjusting for any baseline covariates determined to be confounder, to estimate odds-ratio of probability of mortality between HBOT group and SOC group. We will also report 95% confidence interval of the odds-ratio.

Sample size consideration: Using a sample of 160 patients, 40 in HBOT arm and 120 in SOC arm (post matching) we can detect a reduction of 22.5% with 80% power at significance level of 0.05, assuming that the proportion of mechanical ventilation needed in SOC arm is about 80%.

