### **9.5 Sample Size**

Using a sample of 160 patients, 40 in HBOT arm and 120 in SOC arm (post matching) we can detect a reduction of 22.5% or higher, against the null of no difference, with 80% power at significance level of 0.05, assuming that the mortality rate in SOC arm is about 80%.

For the secondary analysis, our proposed sample of 160 patients will similarly allow us to detect a difference of 22.5% in need for ventilation between HBOT group and SOC group with 80% power. For comparing the continuous outcome of number of days in ventilation, we have 80% power to detect effect size (cohen's d) of 0.51 with 160 patients.

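### The formal SAP is scheduled for the end of an open-label study while the matching of controls is left unsettled, so the primary comparison could be shaped after outcomes are known

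*Combined protocol and SAP*

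**What the plan says.** **Timing.** Section 9.1 states: "A formal SAP will be prepared at the end of the study, the study is non-blinded". Sections 8.12 and 9.4.7.1 have the investigators meet after 10, 20 and 40 patients to look at safety and efficacy by arm, with death and ventilation among the events watched. Section 9.4.7 adds an interim comparison of all endpoints, 10 treated patients against 30 matched charts. Section 9.4.7.2 blinds the statistician, but only for that interim.

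**What is already fixed.** In-hospital mortality is the primary endpoint, tested by chi-squared (9.4.2). "All tests will be two tailed at significance level of 0.05" (9.4.1). The comparison is 40 against 120, matched 3:1 (5.7, 9.3). Section 9.3 lists age, gender, comorbidity and disease severity as matching factors and aligns control eligibility with that of the treated group.

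**What is not settled.**
- *Matching.* The Brief Summary and section 4.1 name age and gender only. The Reference Therapy row of the Protocol Summary says "based on age and gender and if possible underlying medical comorbidities and initial disease severity". Section 9.3 lists all four. No section gives an algorithm, a caliper, or a definition of comorbidity or severity.
- *Adjustment.* Section 9.4.1 adjusts for baseline variables that differ significantly. Section 9.4.2 describes a follow-up logistic model "adjusting for any baseline covariates determined to be confounder", with no list and no criterion.
- *Scale.* Section 9.4.3 log-transforms ventilator days if they look non-normal, without naming the test or threshold.

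Section 9.4.9 marks multiplicity as not applicable.

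**The concern.** In a non-randomised study, selecting the comparison group is the main design decision. Here the control group is retrospective (5.7) and drawn from what section 9.6.1 describes as a large number of eligible charts. Outcomes are already in those charts, and nothing requires controls to be chosen before the outcomes are read. If the document that settles the matching is written last, by people who have seen mortality by arm, the choice among defensible control sets could be influenced by which one gives the better result. The 0.05 level and the 95% interval for mortality assume that one control set was chosen without regard to outcome, and nothing in the plan secures that.

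**Working it through.** **1. The plan's own figure.** Section 9.5 takes 40 treated patients and 120 controls, puts control mortality near 80%, and claims 80% power at the 0.05 level. Its stated effect is: "we can detect a reduction of 22.5% or higher, against the null of no difference". Reading 22.5% as absolute points (80% to 57.5%):

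- pooled rate = (40 × 0.575 + 120 × 0.80)/160 = 0.744
- null standard error = √[0.744 × 0.256 × (1/40 + 1/120)] = 0.0797
- alternative standard error = √[0.575 × 0.425/40 + 0.80 × 0.20/120] = 0.0863
- power = Φ[(0.225 − 1.96 × 0.0797)/0.0863] = Φ(0.797) = 78.7%

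The stated 80% is reproduced to within 2 points. The concern does not touch the power statement.

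**2. One locked control set.** Reject when |z| > 1.96, with z = (x/40 − y/120)/√[p(1−p)(1/40 + 1/120)], where x and y are the deaths and p is the pooled death rate. Summing exact binomial probabilities with 80% mortality in both groups gives a two-sided type I error of 4.98%. The share favouring HBOT is about 3.0%.

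**3. Best of K control sets.** Assumptions: no treatment effect; 80% mortality throughout; each set is 120 charts drawn from the same eligible pool; the most extreme z is kept. Neither K nor the pool size is in the documents, so both are varied.

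| Sets compared (K) | Pool 240 | Pool 600 | Pool 2,000 |
|---|---|---|---|
| 2 | 7.2% | 8.0% | 8.3% |
| 5 | 11.1% | 12.9% | 13.3% |
| 10 | 14.2% | 17.3% | 19.0% |

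A second simulation of 40,000 trials per cell agreed to within half a point (13.7% for five sets from 2,000), hence the rounded ranges of 7% to 8%, 11% to 14% and 14% to 19%. The error in favour of HBOT alone rises from about 3% to between 6.7% and 8.1% at K = 5.

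**4. Covariate choice (follow-up logistic model only).** Keeping the smallest p-value among the chi-squared test and 16 logistic models on four prognostic factors (assumed log odds ratio 0.3 to 0.8 per SD) gives 7.3% to 13.6%. The section 9.4.1 rule behaves differently. With five factors at log odds ratio 0.7 and 2,000 null trials, the smallest-p search gave 11.6% at 80% mortality and 13.8% at 50%, whereas adjusting only for factors with baseline p < 0.05 gave 3.1% and 4.0%. Followed as written, that rule produces no inflation.

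**5. Scale (ventilator days only).** Taking the better of raw and log scale, for log-normal or gamma-shaped durations at 32 against 96 or 40 against 120, gives 6.8% to 7.3%.

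**The case against.** The strongest reply is that section 9 is itself a plan, so the late SAP is not the first statement of the analysis. Endpoint, test, level, ratio and matching factors are written down; the covariate rule in 9.4.1 looks at baseline data and not at outcomes; the log scale for SAE counts is fixed in 9.4.4; and the study calls itself a pilot. Most of this stands, and it narrows the point.

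It rules out three stronger readings that a reader might infer:
- *That the false-positive rate is inflated.* Late timing permits outcome-guided choices but does not show that they will be made. The number of alternatives tried is an assumption.
- *That free choice of covariates undermines the primary test.* Section 9.4.2 makes that test an unadjusted chi-squared. Covariates enter only the follow-up model, and the smallest-p search is a procedure that the protocol does not describe.
- *That transformation could move the mortality result.* Mortality is binary; the open scale question concerns ventilator days.

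What the reply does not answer is control selection. The chi-squared result depends on which 120 charts are compared. Section 9.3 conflicts with the Protocol Summary and section 4.1 on the factors, and even its four factors leave many admissible sets when no algorithm or definitions are given. The statistician's blinding in 9.4.7.2 does not extend to the authors of the final SAP.

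**Conclusion.** The point holds as a risk to the primary comparison through control selection. The 5% level is met by one locked control set (4.98%, treating the matched groups as exchangeable). It could rise to about 7% to 8%, 11% to 14% or 14% to 19% if the best of 2, 5 or 10 sets were kept, at 80% mortality with pools of 240 to 2,000. These are illustrations under assumed numbers of alternatives; the true size cannot be derived from the documents. Effects on the follow-up logistic model (about 7% to 14% under an assumed search, none under the 9.4.1 rule) and on ventilator days (about 7%) are secondary.

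**What to change.** 1. Change section 9.1 so that the SAP is finalised and dated before the 10-patient comparison. The enrolment pause already planned at that stage is a natural deadline.
2. Reconcile the Brief Summary, the Reference Therapy row, section 4.1 and section 9.3 into one matching specification, with a stated algorithm, calipers, and definitions of comorbidity and severity.
3. Select and lock the standard-of-care charts on variables known at the index time, before their outcomes are abstracted. Do this for the 30 interim controls as well as the final 120.
4. Fix the adjustment set for the follow-up logistic model and one scale for ventilator days.

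The cost is doing the same writing earlier, with no added patients, visits or procedures. The change protects the error rate; it does not remove confounding from the non-randomised design.
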